4.6 Lost to Follow-Up

A subject is considered lost to follow-up if he/she repeatedly fails to return to the study site for scheduled visits and is unable to be contacted by the study site. The following actions must be taken if a subject fails to return to the clinic for a required study visit:

- The site must attempt to contact the subject or caregiver and reschedule the missed visit as soon as possible, counsel the subject and/or caregiver on the importance of maintaining the assigned visit schedule, and ascertain whether or not the subject wishes to and/or should continue in the study.
- Before a subject is deemed lost to follow-up, the Investigator or designee must make every effort to regain contact with the subject or caregiver (where possible, 3 telephone calls and, if necessary, a certified letter to the subject's last known mailing address or local equivalent methods). These contact attempts should be documented in the subject's medical record.
- Should the subject or caregiver continue to be unreachable, he/she will be considered to have withdrawn from the study with a primary reason of lost to follow-up. In this case, the discontinuation date will be listed as the date the certified letter was mailed to the subject.

5 Study Treatment

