6.2 Safety Assessments

6.2.1 Adverse Events

All AEs and SAEs will be collected from the time the subject signs the informed consent form (ICF) until the final visit/contact with the subject. AEs that began during the parent study and were ongoing at the end of that study will be reported as ongoing AEs. Additional safety information, including the definition of an AE and the methods for recording, evaluating, and assessing causality of AEs and the procedures for completing and transmitting SAE reports are provided in [Section 8](#).

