7.3 Visits 2 to 13; Treatment Period

Subjects will return to the study site at least every 4 weeks (\pm 3 days) during the 48-week monitoring period. The following assessments will be performed:

- Brief physical exam; Weeks 12, 24, 36 and 48 only
- Vital signs measurements
- Urine pregnancy test (WOCBP)
- Blood sample collection for clinical laboratory tests (serum chemistry and hematology); Weeks 12, 24, 36 and 48 only
- Urinalysis; Week 48 only
- vIGA-AD™ score (excluding subject's scalp)
- %BSA affected calculation (excluding subject's scalp)
- EASI (excluding subject's scalp)

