7.4 Phone Contact at Week 2 (Day 15 ± 3 Days)

Subjects or their caregivers will be contacted by phone at Week 2 to review study drug application instructions, if applicable, and to record AEs and concomitant medication use. Subjects or their caregivers should be reminded to complete their daily diary and bring it with them to the next clinic visit.

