9. STUDY POPULATION

9.1 Subject Disposition

Subject disposition information will be summarized and will include: the number of enrolled subjects, the number of subjects who apply any study medication, the number of subjects who complete the study and who withdraw from the study (together with reasons for withdrawal). The number of subjects whose drug was permanently withdrawn or interrupted due to AE, vIGA-AD™ score or other reasons will also be summarized over the entire study and by visit.

The number of days in the study, defined as the duration between date of study completion / discontinuation (or date of last visit if the study completion/discontinuation date is missing) and the date of Visit 1, will be summarized using descriptive statistics. A figure with Kaplan-Meier curves will also be generated to illustrate this information.

In order to describe the impact of COVID-19 on current study, the following disposition events will be summarized in the tables separately:

- Subjects discontinued from the treatment/study as a result of a positive COVID-19 diagnosis.
- Subjects discontinued from the treatment/study due to other reasons related to COVID-19. This is excluding COVID-19 diagnosis but may include reasons such as site closure, travel restrictions, fear of infection, etc.
- Subjects with study visits altered (including modified in-clinic visit, virtual and phone visits) and missed due to COVID-19.

Previous COVID-19 diagnosis and previous/on-study COVID-19 vaccination, and COVID-19 related protocol deviations will be summarized separately. The impact of COVID-19 (including protocol deviation, visit alteration, treatment/study discontinuation and diagnosis of COVID-19) will also be flagged at subject-level in a data listing. Subject profile will be used to compile all COVID-19 related information for affected subjects.

Also, all COVID-19 related symptoms and confirmed cases that occur during the study will be reported as AEs and included in the summaries.

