For each of these categories, TEAEs will be summarized by SOC in alphabetical order and PT in descending order of frequency. TEAEs ongoing at the end of the previous studies will be considered in the first category (i.e., day of onset ≤ 12 weeks).

At each level of summarization, a subject will be counted once if he/she reported one or more events. The severity of TEAEs and relationship to study drug will be summarized in a similar manner. For summaries of relationship to study drug, a subject will be classified according to related or not related. For summaries of TEAE CTCAE grade, a subject will be classified according to the worst grade.

For treatment-emergent AESIs, summarization will be more extensive, reflecting the more detailed information collected. Information summarized will include number of events per subject, earliest onset day, duration (in days), causality, grade and seriousness of AESIs, outcome, actions taken, assorted physical characteristics of the AESIs, and demographic/baseline characteristics and vIGA-AD™ status of the subjects experiencing them. Each type of AESI will be summarized separately. If a subject has more than one treatment-emergent occurrence of an AESI, the subject's maximum duration, highest levels of causality and seriousness, maximum grade and generally the most extreme level of each characteristic will be summarized. If an AESI was ongoing at end of study (EOS), it will not be included in the duration summary. AESIs ongoing at the end of previous studies will also be included in the summary.

A Kaplan-Meier figure will be generated for each AESI of time to first event for events starting during the study. Time to first onset will be computed as Onset Date of First Occurrence – Date of Visit 1 + 1 if onset date is on or after visit 1 date. Otherwise, time to first onset will be computed as Onset Date of First Occurrence – Date of Visit 1. Subjects not experiencing the AESI will be censored at the date of study completion or discontinuation. AESIs ongoing at the end of the previous studies will not be included.

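### Time to first AESI is censored at a lost subject's certified-letter date, so unobserved time counts as event-free and the AESI Kaplan-Meier curves read slightly low

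*SAP*

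**What the plan says.** SAP 13.2 plans one Kaplan-Meier figure per AESI for time to first event, counted from Visit 1. Its censoring rule is: "Subjects not experiencing the AESI will be censored at the date of study completion or discontinuation". It has no separate rule for subjects lost to follow-up and no fallback when the date is missing.

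Protocol 4.6 calls a subject lost when "he/she repeatedly fails to return to the study site for scheduled visits and is unable to be contacted by the study site". Before that label is applied the site must try to regain contact ("where possible, 3 telephone calls and, if necessary, a certified letter"). If the subject remains unreachable, "the discontinuation date will be listed as the date the certified letter was mailed to the subject". No time limit is set for these steps.

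Under Protocol 6.2.1, adverse events are collected "until the final visit/contact with the subject"; section 8.3.1 ends collection at the final visit. Protocol 7.3 sets the clinic schedule: "Subjects will return to the study site at least every 4 weeks". The one scheduled call between visits is in Protocol 7.4: "Subjects or their caregivers will be contacted by phone at Week 2".

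SAP 9.1 measures days in study to the completion or discontinuation date ("or date of last visit if the study completion/discontinuation date is missing"). That fallback is written for days in study only, and it would not apply to a subject who was sent a letter, because the date is then present.

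**The concern.** A censoring date should be the last day on which the event could have been recorded. The mailing date is an administrative date. Between the last contact and the mailing, nobody asks the subject about adverse events, yet the plan counts the subject as at risk and event-free. The denominator of the Kaplan-Meier estimate is then too large on those days while the numerator is complete only for observed subjects. The error always runs toward a lower AESI curve.

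Safety and tolerability is the first objective, the three AESIs were chosen for their clinical importance, and no statistical testing is planned, so the descriptive curve is itself the result that readers will use.

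**Working it through.** The plan states no AESI rate, loss rate or lag, so there is no figure of its own to reproduce. The check has two parts: how long the gap is likely to be, and what it does to the curve.

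**Length of the gap.** Scheduled visits fall on Days 1, 29, 57, ..., 337, which is 28 days apart with a window of ±3 days at each end.

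- One missed visit: 28 − 6 = 22 to 28 + 6 = 34 days since the last clinic assessment.
- Two missed visits (one reading of a repeated failure to attend): 56 − 6 = 50 to 56 + 6 = 62 days.
- Time for calls and mailing comes on top.
- In the first interval the Week 2 call can shorten the gap: from Day 15 to the missed Day 29 visit is 14 days.

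A lag of 28 to 70 days is therefore a reasonable range, but it is an assumption. The upper end is two missed visits (56 days) plus 14 days for calls and mailing.

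**Effect on the curve.** I used the large-sample limit of the Kaplan-Meier estimate with these assumptions: constant AESI hazard; a fraction L lost, with last contact v spread evenly over Visits 1 to 12; a lost subject kept in the risk set for g days after v with no event recordable.

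- Hazard: h = −ln(1 − p)/337, where p is the true incidence at Day 337.
- Truly observed and event-free at day t: O(t) = [(1 − L) + (L/12) × number of v ≥ t] × exp(−h(t − 1)).
- Unobserved but still counted: U(t) = (L/12) × sum of exp(−hv) over v < t ≤ v + g.
- Events on day t: E(t) = O(t) × (1 − exp(−h)).
- Censoring at last contact multiplies survival by 1 − E/O, which recovers p. The planned rule multiplies by 1 − E/(O + U).

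One day worked out, with p = 20%, L = 10%, g = 56, t = 170:

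- h = −ln(0.8)/337 = 0.000662.
- Five of the possible last contacts are at or after Day 170, so O = (0.9 + 5 × 0.1/12) × exp(−169h) = 0.9417 × 0.8941 = 0.842.
- Last contacts on Days 141 and 169 fall in the gap, so U = (0.1/12) × (0.9109 + 0.8941) = 0.015.
- O/(O + U) = 0.842/0.857 = 0.982. The daily event rate is understated by about 1.8%.

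Multiplying over Days 1 to 337 gives the Week 48 estimate under the planned rule:

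| True incidence | Lost | Lag 28 days | Lag 56 days | Lag 70 days |
|---|---|---|---|---|
| 10% | 5% | 9.96% | 9.92% | 9.91% |
| 10% | 10% | 9.92% | 9.84% | 9.81% |
| 10% | 20% | 9.82% | 9.67% | 9.60% |
| 20% | 5% | 19.92% | 19.85% | 19.82% |
| 20% | 10% | 19.84% | 19.70% | 19.63% |
| 20% | 20% | 19.67% | 19.37% | 19.23% |

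The smallest understatement is 10 − 9.96 = 0.04 points (0.4% of 10%). The largest is 20 − 19.23 = 0.77 points (3.8% of 20%). The largest relative one is 10 − 9.60 = 0.40 points (4.0% of 10%).

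**The case against.** The strongest defence is that little depends on this date. The main AESI results are counts and percentages of subjects, and SAP section 6 takes the total number of subjects as denominator in the adverse event tables. The visible SAP plans no exposure-adjusted event rate, and exposure is derived separately from treatment periods, doses and grams. Subjects who withdraw and attend the Early Termination visit have adverse events recorded there and leave no such gap. The letter goes out only if needed, and sites must try to reschedule a missed visit promptly. All of this stands. It confines the problem to the AESI Kaplan-Meier figures and to lost subjects without the AESI, and it keeps the effect small. It does not remove the error, because following the two texts exactly still keeps unobservable subjects at risk.

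A reader might infer more than the documents support:

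- **That AESI incidence in general is understated.** The crude tables do not use the censoring date.
- **That the bias reaches about 6% of the incidence.** That takes 30% loss and a 70-day lag together (a true 20% would read 18.79%). No document gives a loss rate, and 30% would be high for this one reason for withdrawal.
- **That exposure is inflated.** The unobserved time can be converted to subject-years, but no visible planned rate uses them.
- **That subjects who leave because of skin reactions are being hidden.** That would be informative censoring. Censoring at last contact would not remove it, and the calculation above assumes it away.
- **That SAP 9.1 is wrong too.** Days in study is a disposition measure, explicitly defined by the completion or discontinuation date.

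**Conclusion.** The concern holds for the AESI Kaplan-Meier curves. The mechanism follows from the text, and its direction does not depend on the assumed rates: time without adverse event collection counts as event-free, so the curves read low. The size is modest. It is about 0.04 to 0.8 percentage points at Week 48, or about 0.4% to 4% relative, if the 48-week incidence is 10% to 20%, 5% to 20% of subjects are lost, the lag is 28 to 70 days, the hazard is constant and loss is unrelated to the AESI. All of these are assumptions.

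The rule also leaves two cases undefined. A lost subject who was never sent a letter has no stated discontinuation date. At the interim analysis, for which SAP 10.5 plans all summaries, ongoing subjects have neither a completion nor a discontinuation date. This is a correction worth making before database lock; it does not put the study's conclusions in doubt.

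**What to change.** In SAP 13.2, censor subjects without the AESI at the earlier of (a) the study completion or discontinuation date and (b) the last visit or contact at which adverse events were assessed. Where (a) is missing, use (b). If contact dates are not held in the CRF, which is not available for this review, use the last recorded visit date for (b).

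The cost is one sentence and one derived date. No protocol change is needed: the letter date remains the disposition date, and SAP 9.1 is unchanged. A footnote should say that, for lost subjects, AESI follow-up time can be shorter than days in study. The AESI curves will be slightly higher. If only visit dates are available, a subject last reached by the Week 2 call is censored a little early.

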13.4 Clinical Laboratory Evaluation

All clinical laboratory (hematology, clinical chemistry, and urinalysis) values will be listed by treatment group and subject. The reference normal ranges and reference range indicators (e.g., high, low, normal) will be supplied by the central laboratory and displayed in the data listings. Values outside the normal range for chemistry and hematology laboratory parameters will be

flagged. Change from baseline in abnormality status will be summarized using shift tables by visit. For quantitative measures, observed values and change from baseline in clinical laboratory values will be summarized descriptively by visit.

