6.2.4 Clinical Safety Laboratory Assessments

All protocol-required laboratory assessments must be conducted in accordance with the Study Reference Manual or Laboratory Manual and the protocol Schedule of Assessments ([Table 1](#)). Laboratory requisition forms must be completed, and samples must be clearly labeled with the subject number, protocol number, site number, and visit date. Details for the preparation and shipment of samples will be provided by the laboratory and are detailed in the Study Reference Manual or the Laboratory Manual. Reference ranges for all safety parameters will be provided to the site by the laboratory responsible for the assessments.

A list of clinical laboratory tests and parameters is provided in [Table 3](#).

All laboratory tests with values that are considered clinically significantly abnormal during participation in the study should be repeated until the values return to normal or Baseline. If such values do not return to normal within a period judged reasonable by the Investigator, the etiology should be identified, if possible, and the Sponsor and Medical Monitor notified.

Table 3: Laboratory Tests

Diagnostic Tests		

• All subjects
• Urine pregnancy tests (WOCBP only)^a• Direct-Enrolling Subjects Only
• Serum pregnancy test at Screening (WOCBP only)• HBsAg• Hepatitis C antibody• Anti-HBc• Anti-HBs^b• At the Investigator's discretion, subjects may be screened for alcohol and illicit drug use.		
Serum Chemistry		

• BUN• Creatinine• Glucose (fasting not required)• Sodium• Potassium• Chloride	
• Total carbon dioxide• Calcium• AST• ALT• Alkaline phosphatase	
• Uric acid• Total bilirubin (+fractionated if required)• Total protein• Albumin
Hematology		

• Platelet count• RBC count• WBC count (absolute)• Reticulocyte count• Hemoglobin• Hematocrit	
• RBC Indices:
• MCV• MCH• MCHC• Reticulocyte percentage	
• WBC Differential:
• Neutrophils• Lymphocytes• Monocytes• Eosinophils• Basophils

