7.6 Unscheduled Visits

Unscheduled visits may occur, as needed. For subjects who experience suspected disease worsening (vIGA-AD™ ≥ 2) between scheduled study visits may contact the study site to arrange an unscheduled visit (see Section 5.1.5.2). The following assessments may be performed:

- Brief physical exam
- Vital signs measurements
- Urine pregnancy test (WOCBP)
- Blood sample collection for clinical laboratory tests (serum chemistry and hematology)
- Urinalysis
- vIGA-AD™ score (excluding subject's scalp)
- %BSA affected calculation (excluding subject's scalp)
- EASI (excluding subject's scalp)
- [REDACTED]
- PP-NRS (by subject or caregiver)
- [REDACTED]
- AE recording
- Concomitant medication recording
- Collect and review subject diaries for treatment compliance, if applicable
- Dispense subject diaries, if applicable
- Collect and dispense study drug, if applicable
- Review instructions on how to apply study drug, if applicable
- Study drug application under supervision, if applicable

If disease worsening is confirmed, a new treatment course will be initiated.

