10.4.3 Safety Analyses

The ITT Population will be used in the analysis of safety data. Summaries will be presented overall and by the following categories: received tapinarof treatment in either DMVT-505-3101 or DMVT-505-3102; received vehicle treatment in either DMVT-505-3101 or DMVT-505-3102; received tapinarof treatment in DMVT-505-2104; and enrolled directly into DMVT-505-3103.

The number and percent of subjects with TEAEs will be summarized by system organ class, and preferred term for all TEAEs, all TEAEs considered by the Investigator to be related to study drug, all SAEs, all TEAEs leading to study drug discontinuation, and all TEAEs leading to study discontinuation. TEAEs will be defined as follows:

- For rollover subjects, all AEs reported in DMVT-505-3103 will be considered to be a TEAE except for those AEs ongoing at the end of the parent study (DMVT-505-3101, DMVT-505-3102, or DMVT-505-2104) but resolved prior to the Visit 1 date in DMVT-505-3103.
- For subjects enrolled directly into DMVT-505-3103, all AEs that start after the first dose of study medication will be considered to be a TEAE.

Data listings will be provided for subjects who discontinued the study due to an AE and for subjects with an SAE.

Laboratory values will be classified as normal, low or high based on normal ranges supplied by the laboratory. Changes from Baseline in abnormality status will be summarized using shift tables. For quantitative laboratory measures, observed values and changes from Baseline will be summarized descriptively by visit.

Observed vital sign values (systolic and diastolic blood pressure, pulse rate, and body temperature) and change from Baseline in vital signs will be summarized similarly to the laboratory values.

LTS scores will be summarized by visit for subject (or caregiver) overall assessment and Investigator overall assessment separately.

• [REDACTED]
[REDACTED]
[REDACTED]
[REDACTED]
[REDACTED]
[REDACTED]
10.4.5 [REDACTED]
[REDACTED].

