Efficacy and safety endpoints will be summarized according to the nominal visit as assigned by the investigator except for assessments collected on early termination visits. Early termination visit will be assigned based on the last nominal visit across all procedures and assessments and re-numbered to the last nominal visit number + 1. For example, if a subject attended Visit 1 (Baseline), Visit 2 (Week 4), Visit 3 (Week 8) and then early terminated, the early termination visit will be re-numbered and analyzed as Visit 4 (Week 12).

Unscheduled visits will not be re-numbered and will not be included in OC summaries but will be included in listings. Unscheduled visits will be included in the LOCF imputation by using

target day listed in the Visit Terminology table; for missing visits LOCF values will be based on scheduled and unscheduled visits occurring on or before target day.

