10.4 Handling of Dropouts or Missing Data

Efficacy endpoints will be summarized by visit using OC. Additionally, efficacy endpoints will be summarized by visit using LOCF to impute missing data. LOCF will include scheduled and unscheduled visits. Baseline values will not be carried forward.

Average weekly PP-NRS scores will be calculated for all nominal visits as the average of 7 daily post-baseline PP-NRS scores prior to and including the values assessed on the visit date. If daily PP-NRS scores are missing for more than 3 days in a 7-day period, the average weekly PP-NRS score will be set to missing. If two or more scores are reported on the same day, the maximum score on that day will be used.

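### Laboratory summaries follow nominal visits only, so no table counts subjects abnormal at any time and unscheduled values reach listings alone

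*SAP*

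**What the plan says.** SAP 13.4 specifies two laboratory summaries. The first is categorical: "Change from baseline in abnormality status will be summarized using shift tables by visit". The second is continuous: "For quantitative measures, observed values and change from baseline in clinical laboratory values will be summarized descriptively by visit". The categories come from Protocol 10.4.3: "Laboratory values will be classified as normal, low or high based on normal ranges supplied by the laboratory". SAP 13.4 also lists every laboratory value and flags chemistry and hematology results outside the normal range.

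The meaning of a visit is set in SAP 7: "Efficacy and safety endpoints will be summarized according to the nominal visit as assigned by the investigator". The one stated exception is the early termination visit, which is given the number after the subject's last nominal visit. For other off-schedule contacts SAP 7 says: "Unscheduled visits will not be re-numbered and will not be included in OC summaries but will be included in listings". It then admits unscheduled data to LOCF imputation, and SAP 10.4 states the scope of LOCF: "Additionally, efficacy endpoints will be summarized by visit using LOCF to impute missing data".

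Off-schedule blood samples are foreseen. Protocol 6.2.4 says that clinically significant abnormal tests "should be repeated until the values return to normal or Baseline", and Protocol 7.6 lists chemistry and hematology among the assessments that may be done at an unscheduled visit.

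**The concern.** Change from Baseline in laboratory values is a stated safety endpoint. The sample size rests on long-term safety exposure, and Protocol 10.5 foresees a data cut to support the marketing application. A reader of the safety results will ask two things of the laboratory data: how many subjects became abnormal at any time, and how far the values went. The planned tables do not answer the first. They answer the second only through per-visit extremes.

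The plan uses worst-case summaries elsewhere. SAP 13.2 classes each subject by worst CTCAE grade for TEAEs and by the most extreme characteristic for adverse events of special interest. SAP 13.5 tabulates markedly abnormal changes in vital signs. Laboratory data have no equivalent.

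**Working it through.** The plan gives no figure to reproduce. The check sets the sections side by side.

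1. **Which samples enter a laboratory table.** Protocol 7.3 schedules blood draws at Weeks 12, 24, 36 and 48, and Protocol 7.5 adds Week 49. These have nominal visit numbers and are tabulated. Early termination samples are tabulated under the next visit number. For a subject whose last visit was Week 12 that is Week 16, where no draw is planned. Unscheduled samples keep no visit number, so a table by nominal visit has no column for them.

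2. **Whether another route brings unscheduled samples in.** LOCF is the only summary in which SAP 7 uses unscheduled data, and SAP 10.4 specifies it for efficacy endpoints. SAP 13.4 mentions neither LOCF nor any worst-value or any-time summary. What remains is the listing.

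3. **Whether the by-visit tables can be combined into an any-time count.** Suppose that the same number *n* of subjects with a normal Baseline value are high at each of the five scheduled draws. If they are the same people each time, *n* were ever high. If they are different people each time, 5 × *n* were ever high. The five tables look identical in both cases, so the any-time count cannot be recovered even when there are no unscheduled samples.

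4. **What an off-schedule peak looks like in the output.** Take a hypothetical subject whose ALT is normal at Baseline, Week 12 and Week 24 and high at an unscheduled Week 18 draw. The Week 12 and Week 24 shift tables both show normal to normal. A shift to the highest post-Baseline value would show normal to high.

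5. **What is known about magnitude.** Low, normal and high put ALT at 1.1 × ULN and at 10 × ULN in one cell. SAP 6 requires minimums and maximums for continuous variables, so an extreme value at a nominal visit is visible as that visit's maximum. One maximum does not say how many subjects exceeded a level.

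6. **The adverse event route.** Protocol 8.1.1 makes an abnormal result an AE when the investigator considers it clinically significant, with an exception for findings associated with the underlying disease. Such events enter the TEAE tables by maximum CTCAE grade. Values not judged clinically significant do not.

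**The case against.** The strongest reply is that little is lost, and parts of it stand.

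- **Repeat tests largely share the AE trigger.** Protocol 6.2.4 requires repeats only for values considered clinically significant, which is close to the judgement that creates an AE. Many subjects with mandated repeats will therefore appear in the TEAE tables. This narrows the gap. It does not supply a laboratory count that is independent of that judgement.
- **A repeat often follows an abnormal scheduled value.** That subject is already shown as abnormal at that visit, and only a later, more extreme value would be missed. A reader might infer that unscheduled draws usually hold the worst value. The documents do not support that, since repeats continue until recovery and many will be lower.
- **The exclusion is partly inferred.** SAP 7 removes unscheduled visits from OC summaries, and SAP 13.4 does not use that label. The reading rests on the laboratory tables being observed-value summaries by nominal visit, which SAP 7 states for safety endpoints.
- **Nothing is contradicted or hidden.** Protocol 10.4.3 and SAP 13.4 agree, the study is descriptive, and every value is listed. But with up to 961 subjects a listing is not a count.

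A reader might also take 2.0 × ULN for ALT/AST and 1.5 × ULN for bilirubin as the protocol's laboratory safety thresholds. They are not. Protocol 4.3 uses them as entry criteria for direct-enrolling subjects only, about 125 of up to 961, and the bilirubin rule has an exception based on the direct fraction.

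**Conclusion.** The point holds as a gap in the laboratory summaries. The plan does not report how many subjects were abnormal at any time, and an abnormal or peak value at an unscheduled draw is in no laboratory table. The tables can therefore understate abnormality on a stated safety endpoint. This rests on reading the SAP 7 rule for nominal visits as governing SAP 13.4. It also assumes that no laboratory analysis sits in text absent from the public SAP, whose numbering passes from 13.2 to 13.4.

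The size cannot be given. A reader might reason from the 12-week spacing that an excursion of *D* weeks, timed at random, meets a scheduled draw with probability *D*/12. For 2, 4 and 6 weeks that is 2/12 = 17%, 4/12 = 33% and 6/12 = 50%, so 50% to 83% would be missed. That range does not measure this gap. It describes all excursions of an assumed length, including those at which no blood was drawn and which no table could recover. For an excursion seen only at an unscheduled draw, absence from the laboratory tables is certain by construction. What matters is how many such subjects there are. The documents give neither that number nor typical durations, and it could be small.

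The stronger reading that the plan cannot show magnitude at all also fails, because by-visit maximums do so at nominal visits. This is a worthwhile, inexpensive improvement and not an error in the plan.

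**What to change.** Keep the by-visit tables. Add to SAP 13.4 one shift table from Baseline to the worst post-Baseline value, with lowest and highest shown separately, using all scheduled, unscheduled and early termination samples. Footnote the number of subjects with any unscheduled sample.

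Optionally, add a count of subjects by worst post-Baseline ALT, AST and total bilirubin, in pre-specified multiples of ULN or by CTCAE v5.0 grade, which the protocol already uses for AEs. Present these as descriptive categories, and do not describe the entry limits in Protocol 4.3 as on-study thresholds.

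The cost is one table, or two with the option, from data already collected, with no change to study conduct. The drawback is that subjects with more draws have more chances of an abnormal value, which the footnote lets the reader judge.
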